#### 7.7.1.2 Subgroups

Descriptive summaries and MMRM models will be provided for subset 1 plasma biomarkers for subgroups of APOE e4 status (e4 carrier, non-e4 carrier), gender (male, female), age group (< 65 years, ≥ 65 years), AD diagnosis (mild cognitive impairment, mild dementia) (Table 7-25) in the FAS. Listings for the main estimand will be provided for plasma and CSF biomarkers [subsets 1 and 2], volumetric MRI parameters [subset 1], amyloid PET parameters [subsets 1 and 2], and Tau PET parameters [subset 1] (Table 7-26).

#### 7.7.2 Correlation with CDR-SB Objective

Treatment-related association between CFB in biomarker levels (CSF, plasma, amyloid PET and Tau PET) [subset 1] in Table 7-25 and CFB in CDR-SB will be assessed. Specifically, the following analyses will be conducted for the main estimand [Table 7-27].

- Adjusted correlative analyses of CFB in CDR-SB and CFB in specified subset 1 biomarkers. Three MMRM models will be assessed.
  - o Model 1 of CFB in biomarker with treatment group, categorical visit, visit-by-treatment interaction, baseline biomarker, and APOE e4 status as fixed effects.
  - o Model 2 of CFB in CDR-SB with the same fixed effects terms as in model 1, and baseline CDR-SB as additional fixed effects term.
  - o Model 3 of CFB in CDR-SB with the same fixed effects terms as in model 1, and baseline CDR-SB and CFB in biomarker as additional fixed effects terms.
  - o The three models include only participants with both CFB in CDR-SB and CFB in biomarker at matching timepoints.
  - Similar analyses will be repeated with the following treatment groups in the model: AL002 15 mg/kg group, AL002 40 and 60 mg/kg combined group, and placebo group. Statistics from fitting the MMRM model will be reported only for the AL002 40 and 60 mg/kg combined group (or its comparison to placebo).
- Group-level scatterplots of adjusted mean difference from placebo in CDR-SB and adjusted mean difference from placebo in specified subset 1 biomarkers at matching timepoints.
  - The adjusted mean difference from placebo is the least squares mean difference (vs. placebo) in the corresponding MMRM analyses.

Protocol No. AL002-2 Last Revision Date: 12 Aug 2025

- o Add the error bars (±SE) for adjusted mean difference from placebo in CDR-SB.
- o Include AL002 40 and 60 mg/kg combined group in the scatterplot.
- o Add Pearson and Spearman correlation coefficients, and linear regression line (exclude the combined group AL002 40 and 60 mg/kg).

For subset 1 Tau PET parameters in Table 7-25, a sensitivity analysis will be additionally conducted with similar analyses for the subset with redefined baseline.

#### 7.7.3 Baseline Plasma pTau217 as Disease Staging Variable Objective

Subgroup analyses of CFB in COAs (primary and secondary endpoints) with subgroups based on baseline plasma pTau217 terciles will be conducted similarly as described in Section 7.4.1.2 using pMMRM and MMRM models for the main estimand [Table 7-25]. Baseline plasma pTau217 tercile subgroups are defined as below:

- Low expression (levels  $\leq 1^{st}$  tercile cutpoint)
- Medium expression (1st tercile cutpoint < levels  $\leq 2^{nd}$  tercile cutpoint)
- High expression (levels > 2nd tercile cutpoint)

Subgroup analyses of CFB in subset 1 plasma biomarkers subgroups based on baseline plasma pTau217 terciles will be conducted using MMRM for the main estimand [Table 7-28].

#### 7.7.4 Miscellaneous

Demographics and baseline characteristics will be summarized by treatment group, AL002 40 and 60 mg/kg combined group, total AL002 group, and overall for FAS subsets of participants with amyloid PET data, Tau PET data (at least one evaluable baseline or post-baseline PET scan), and CSF data (at least one evaluable baseline or post-baseline CSF measurement for the subset 1 CSF biomarkers) to assess the representativeness of these subsets to the FAS.

A listing will be provided for the amyloid probability score (APS), derived from the PrecivityADTM algorithm that combines A $\beta$ 42/40, APOE genotype and age, for the randomized participants with test results.

#### 7.8 Immunogenicity Endpoints

The exploratory analyses for immunogenicity endpoints will be performed on all randomized participants who received at least one dose of study drug and had at least one post-baseline sample evaluable for immunogenicity.

#### 7.8.1 Antidrug Antibodies (ADAs)

Blood serum samples will be collected for determination of ADAs. In addition to titer numerical results, blood serum results will be classified as Positive, Negative or Unknown (missing, non-evaluable, etc.).

The number and percentage of participants having Positive or Negative results will be summarized by visit (refer to Table 7-12 for analysis visit window definition) and treatment group. The titer numerical results will be summarized with median, minimum, and maximum by visit and treatment group.

Protocol No. AL002-2 Last Revision Date: 12 Aug 2025

Shift from baseline in blood serum classes will be summarized by visit (refer to Table 7-12 for analysis visit window definition) and treatment group using the frequency count and percentage of participants in each category.

A listing of ADAs will be provided.

#### 7.9 Summaries for APOE e4-Homozygous Participants Set (e4/e4 Set)

In addition to the participant disposition specified in Section 7.2.1 and MRI findings specified in Section 7.5.7, the demographics and baseline characteristics specified in Section 7.3.1 and the summary of AEs and TEAE by SOC, PT and severity specified in Section 7.5.2 will be summarized using descriptive statistics for the e4/e4 Set (Section 5.4). In addition, swim lane plots of ARIA-E and ARIA-H events over time since the first study drug administration (in days) will be provided for the e4/e4 Set. All byparticipant data listings will be provided for the ARS (unless otherwise specified) which already include the e4/e4 participants. So, no separate listings will be provided for the subset.

Protocol No. AL002-2 Last Revision Date: 12 Aug 2025

## 8. ANALYSES PERFORMED BEFORE DATABASE CLOSURE

The database lock will occur when all participants either completed or prematurely discontinued the planned study treatment period of this study. No efficacy interim analyses will be conducted prior to the database lock of the study.

Protocol No. AL002-2 Last Revision Date: 12 Aug 2025

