3.2.2. Treatment Period Termination Date

A treatment period termination date (TPTD) is defined as the single, cross-study date that is the end of the treatment period for all participants in the study. For participants who did not pause or discontinue dosing, the TPTD will determine the last date they may receive a dose of study drug; an EFU visit (if applicable) and an SFU visit (if applicable) will follow any final dosing visit that occurs for that participant. For participants who had paused dosing or who had discontinued dosing, the TPTD still defines the end of their planned treatment period, and an EFU visit (if applicable) and an SFU visit (if applicable) will follow the end of the planned treatment period for that participant.

The TPTD for all participants in the study will be based on the date when the last randomized participant receives the first dose of study drug on their Day 1 Visit, and the TPTD will occur 48 weeks from that date (ie, the TPTD is the projected Week 49 Visit for the last participant randomized). All study sites will be informed of the TPTD when the last randomized participant receives their first dose of study drug, as that will determine when all participants in the study will receive their last dose of study drug.

All participants must have their final visit of their treatment period (whether dosed with study drug or not) on or before the TPTD, and all visits after the TPTD will be follow-up. In the event that the visit window (+5 days) for a given participant falls after the TPTD, it will be modified

AL002 Alector, Inc.

for this participant such that the visit window will instead end on the TPTD. This will ensure the final visit of the treatment period, for all participants, will be on or before the TPTD.

All participants who are consent and meet the eligibility criteria for the AL002-LTE study will have the opportunity to be enrolled in the AL002-LTE study at their final visit of the treatment period (refer to the study protocol of the AL002-LTE study for more details). For participants who completed 96 weeks of treatment, enrolling in the AL002-LTE study would occur at their Week 97 Visit. For participants who did not complete 96 weeks of treatment but were still on treatment at their final visit of the treatment period on or before the TPTD, they will have the opportunity to be enrolled in the AL002-LTE study at their final visit of the treatment period on or before the TPTD.

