3.3.4. Follow-Up Visits

When a randomized participant completes all study visits and procedures up to and including the final visit of their planned treatment period, an SFU visit will follow 8 weeks after this last treatment period visit, unless the participant enrolls in the AL002-LTE study. The end of a given participant's planned treatment period is defined by the TPTD as noted above. For participants who had paused dosing or who had prematurely discontinued dosing, the TPTD as noted above, will still define the end of their planned treatment period. The SFU visit will follow 8 weeks after the end of the planned treatment period for each participant, unless the participant enrolls in the AL002-LTE study. If a participant enrolls in the AL002-LTE study, an SFU visit is not required.

An EFU visit may or may not be required for a given participant, who has completed the planned treatment period and does not enroll in the AL002-LTE study. If a participant enrolls in the AL002-LTE study, an EFU visit is not required. For participants who do not enroll in the AL002-LTE study, an EFU visit is required 4 weeks prior to the SFU visit if the final COA and biomarker assessments were not completed within the defined time intervals as follows:

- An EFU is required if the last COA visit was done more than 12 weeks since the date the EFU visit would occur.
- An EFU visit is required if the last LP was done more than 12 weeks since the date the EFU visit would occur.
- An EFU is required if the last Amyloid PET or Tau PET was done more than 24 since the date the EFU visit would occur.

If the COA, LP, or PET biomarker assessments were not collected in the specified time period noted above, the participant will need to complete an EFU visit 4 weeks prior to the SFU visit.

An ET visit is performed only in cases where participation is permanently discontinued. If the participant withdraws or is discontinued from the study for any reason, the ET is completed 8 weeks after the last administered dose. Participants who complete an ET visit will not require a SFU visit, if the safety assessments were collected at a regularly scheduled study visit 8 weeks after the final dosing visit. Similarly, to the EFU visits for those who have completed the planned treatment period, the following efficacy and biomarkers are required as part of the ET visit if the following conditions are met:

COA visit was done more than 12 weeks since the date the ET visit would occur.

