12.2. Study Termination

Although Alector has every intention of completing the study, Alector reserves the right to discontinue the study at any time for clinical or administrative reasons.

The end of the study is defined as the date on which the last participant completes the last visit (includes SFU visit).

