#### 3.1.3 Treatment Duration

The total duration of study participation for each participant will be up to approximately 115 weeks. This includes the screening period of up to 8 weeks prior to the optional Predose Baseline visit or to Day 1 visit, an optional Predose Baseline visit of up to 21 days prior to Day 1 visit, a treatment period of a minimum of 48 weeks and a maximum of 96 weeks, a possible final efficacy follow-up (EFU) visit 4 weeks after the last study drug administration, and a mandatory safety follow-up (SFU) visit approximately 8 weeks after the last study drug administration. An EFU visit will be required for a given participant only if a minimum number of weeks have elapsed since the previous efficacy assessments (COAs, fluid and imaging biomarkers) for that participant. Please see the Schedules of Assessments in the protocol for details on when an EFU visit is required.

The treatment period for each participant in this study will be a minimum of 48 weeks and a maximum of 96 weeks, with treatment duration varying for each participant. The earliest randomized participants will have a treatment period of 96 weeks and the last randomized participants will have a treatment period of approximately 48 weeks.

A treatment period termination date (TPTD) is defined as the single, cross-study date that is the end of the treatment period for all participants in the study. The TPTD for all participants in the study will be based on the date when the last randomized participant receives the first dose of study treatment on their Day 1 visit and the TPTD will occur 48 weeks from that date (i.e., the TPTD is the projected Week 49 visit for the last participant randomized). All study sites will be informed of the TPTD when the last randomized participant receives their first dose of study drug, as that will determine when all participants in the study will receive their last dose of study drug.

All participants must have their final visit of their treatment period (whether dosed with study drug or not) on or before the TPTD, and all visits after the TPTD will be follow-up. In the event that the visit window (+5 days) for a given participant falls after the TPTD, it will be modified for this participant such that the visit window will instead end on the TPTD. This will ensure the final visit of the treatment period, for all participants, will be on or before the TPTD.

Protocol No. AL002-2 Last Revision Date: 12 Aug 2025

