#### **6.3.2.1** Treatment-Emergent Adverse Events

- If both the start time of the AE and the time of the first study drug administration are available, an AE is considered a TEAE if its start date and time are after the first study drug administration start time and no later than 90 days after the last dose date. The last dose date is defined in Section 7.1.1.1.
- If either the start time of the AE or the time of the first study drug administration is unavailable, an AE is considered a TEAE if its start date is on or after the first dose date and no later than 90 days after the last dose date. Handling of incomplete dates is specified in Section 6.3.2.6.

Protocol No. AL002-2 Last Revision Date: 12 Aug 2025

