## 7.1.1.2.1 Efficacy Data

Efficacy endpoints are scheduled to be performed or collected at nominal visits per protocol: Screening, Week 25, Week 49, Week 73, Week 97, early termination (ET), and EFU (only collected if COA is not performed or collected within 12 weeks since the last COA collection). For the efficacy endpoints, assessments will be allocated to analysis visits using the analysis visit window intervals in which they fall in as specified in Table 7-1.

Efficacy data will be summarized based on the analysis visits (hereinafter may be referred to as "visit"), when applicable.

Table 7-1. Analysis Visit Windows for Efficacy Assessments

Nominal Visit per Protocol	Targeted Day of Nominal Visit (Based on Study Day)	Analysis Visit	Analysis Visit Window (Based on Study Day)
Scree			
Screening	-	Baseline b	~ 1
Treati	nent Phase	Baseline	≤1
Week 1 a	1		
Week 25	169	Week 24	[2, 253]
Week 49	337	Week 48	[254, 421]
Week 73	505	Week 72	[422, 589]
Week 97	673	Week 96	≥ 590

<sup>a COAs are scheduled to be performed/collected prior to dosing.

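### SAP Section 8 sets database lock at the end of the treatment period, which read literally comes before follow-up visits that the SAP's own analyses use

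*SAP*

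**What the plan says.** SAP Section 8 gives a single condition for lock: "The database lock will occur when all participants either completed or prematurely discontinued the planned study treatment period of this study". It mentions no follow-up visit, data cut-off or second lock.

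The treatment period ends for everyone still in the study no later than the TPTD. Protocol Section 3.2.2 (repeated in SAP Section 3.1.3) states that "all visits after the TPTD will be follow-up". SAP Section 3.1.3 then schedules "a possible final efficacy follow-up (EFU) visit 4 weeks after the last study drug administration". The same section makes the SFU compulsory and places it at about 8 weeks from the final dose. Protocol Section 3.3.4 counts both visits from the end of the treatment period and waives them for anyone who enters the LTE. It adds: "An EFU is required if the last COA visit was done more than 12 weeks since the date the EFU visit would occur".

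The SAP uses data from beyond the treatment period in several places:

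- Section 7.1.1.2.1 lists the early termination (ET) visit and the EFU among the sources of efficacy data and allocates efficacy assessments through Table 7-1.
- Section 6.2.1.2 keeps primary-estimand data until 37 days after premature drug discontinuation.
- Section 7.4.1.4 imputes monotone missing CDR-SB up to the TPTD plus 37 days.
- Section 6.3.2.1 counts adverse events as treatment-emergent if they start "no later than 90 days after the last dose date". Section 7.1.1.2.2 uses the same 90-day limit for safety and PK visit windows.
- Sections 6.3.2.6 and 7.1.4.2 give handling rules that name EFU, SFU and ET records.

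**The concern.** As worded, the lock condition is met at about the TPTD, while some required visits are still to come. An analyst who applied Section 8 literally would lock before data existed that other sections of the same SAP tell them to analyse.

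Two kinds of data are exposed. The first is the EFU CDR-SB, which for some participants is the only scheduled value in the Week 72 or Week 96 window. Those visits are already the sparsest: the sample-size section assumes 44% missing at month 18 and 58% at month 24. The second is off-drug safety follow-up to the SFU, for everyone who finishes at the common close and does not enter the LTE.

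Disposition is affected too. SAP Section 7.2.1 tabulates study completers by whether they rolled over into the LTE, and Protocol Section 6.11 counts completion through the SFU. For a non-LTE participant finishing at the TPTD, that status is not known when the trigger is met.

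The protocol cannot be relied on to settle the matter, because SAP Section 1 gives the SAP precedence where the two differ. SAP Section 9 does not list lock timing among its changes.

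**Working it through.** **1. The plan's own duration.** Screening 8 weeks, predose baseline 21 days (3 weeks), treatment up to 96 weeks, SFU at 8 weeks: 8 + 3 + 96 + 8 = 115 weeks. This reproduces the stated figure of approximately 115. The treatment period ends at 8 + 3 + 96 = 107 weeks, so follow-up accounts for the last 8.

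**2. Follow-up relative to the trigger.** The TPTD is the projected Week 49 visit of the last participant randomised, so the condition on all participants is met at about the TPTD. Visits are 28 days apart and the final one must be on or before the TPTD, so a common-close participant's final visit falls 0 to about 28 days before it. Ignoring the ±5-day window:

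- EFU = final visit + 28 days, which is about 0 to 28 days after the TPTD.
- SFU = final visit + 56 days, which is about 28 to 56 days after the TPTD.

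**3. Who needs an EFU CDR-SB.** CDR is scheduled post-baseline at Weeks 25, 49, 73 and 97 (Protocol Table 9). For a final visit at Week W, the EFU is at Week W + 4, and the gap is W + 4 minus the week of the last scheduled CDR. Clinical assessments are due at the EFU if the gap exceeds 12 weeks. EFU study day = (W + 4 − 1) × 7 + 1.

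| Final visit (week) | Last scheduled CDR (week) | Gap to EFU (weeks) | EFU due? | EFU study day | Table 7-1 window |
|---|---|---|---|---|---|
| 49, 53, 57 | 49 | 4, 8, 12 | No | – | – |
| 61, 65, 69 | 49 | 16, 20, 24 | Yes | 449, 477, 505 | Week 72 [422, 589] |
| 73, 77, 81 | 73 | 4, 8, 12 | No | – | – |
| 85, 89, 93 | 73 | 16, 20, 24 | Yes | 617, 645, 673 | Week 96 (≥ 590) |
| 97 | 97 | 4 | No | – | – |

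For the six final visits marked Yes, the previous scheduled CDR-SB falls in an earlier analysis window. The EFU is therefore the only scheduled value for its window, and without it that visit is missing.

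**4. Would the SAP otherwise keep these data?** EFU at 28 days, or 28 + 5 = 33 with the visit window: within 37 days. SFU at 56 days: within 90 days. Both are inside the SAP's own limits.

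**5. Which estimand is touched.** If the participant never stopped drug early, or stopped no more than 37 days before the EFU, the EFU value belongs to the primary estimand. If drug stopped earlier than that, Section 6.2.1.2 already sets the value to missing for the primary estimand. It then matters only for the treatment-policy supportive estimand of Section 6.2.1.3.

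**The case against.** The best reply is that Section 8 is one loosely worded sentence whose purpose is to say that no efficacy interim analysis precedes lock. It sets no data cut-off and excludes no visit. The rest of the SAP plainly expects EFU, SFU and ET records in the database. Read as a whole, the plan probably means to lock after follow-up, and in practice lock may come later than the trigger. This stands as an argument about likely intent. It does not remove the conflict, because the only stated condition for lock is met before the data that the other sections call for.

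Several stronger readings are tempting, and the documents do not support them:

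- **That follow-up data will be discarded.** Nothing says so. The loss follows only if lock is taken at the moment the trigger is met. The documents also refer to a final database lock without saying when it occurs.
- **That half of common-close participants lose a primary value.** Six of the 12 possible common-close final visits (Weeks 49 to 93) require an EFU CDR-SB, but these are calendar slots, not people. LTE enrollees have no EFU. Participants who reached Week 97, or left, well before the TPTD would already have their follow-up recorded.
- **That every lost EFU value is primary data.** The 37-day rule already removes those from participants who stopped drug longer ago.
- **That Protocol Section 12.2 contradicts SAP Section 8.** It defines the end of the study, including the SFU, and not database lock. The contradiction lies inside the SAP; Section 12.2 only supplies a convenient anchor for the fix.
- **That the 90-day adverse-event window requires 90 days of follow-up.** It is an upper limit on attribution and runs 90 − 56 = 34 days past the SFU whenever lock occurs.

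**Conclusion.** The inconsistency is real and Section 8 should be corrected. On its literal wording the lock condition is met before the EFU and SFU of non-LTE participants who finish at the TPTD, and also before the ET visit of anyone who withdraws close to that date.

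What could be lost is (a) the only scheduled Week 72 or Week 96 CDR-SB for non-LTE common-close participants with a final visit at Week 61, 65, 69, 85, 89 or 93, and (b) up to about 56 days of safety follow-up per non-LTE participant finishing at the TPTD.

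The number of participants cannot be derived, since it depends on the accrual pattern and LTE uptake, and neither is given. No loss of power can be calculated either: the sample-size section does not say whether EFU values were counted in its missing-data assumptions. Whether an EFU is due depends largely on the randomisation date, so the main expected cost is precision, together with incomplete safety follow-up. A bias in the treatment comparison is not shown.

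The result assumes visits on the nominal 4-week grid. The ±5-day window could move an EFU to either side of the TPTD when the final visit is nearly 4 weeks before it. It could also tip final visits at Weeks 57 and 81, where the gap is exactly 12 weeks, into needing an EFU.

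**What to change.** Replace the lock condition in SAP Section 8 with one sentence: database lock follows the last participant's last AL002-2 visit, meaning the EFU, SFU or ET visit, whichever is last, or entry into the LTE. This agrees with the protocol's end-of-study definition and with the 37-day and 90-day rules elsewhere in the SAP. It needs no new data and no change of method.

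The cost is a lock about 8 weeks after the TPTD instead of at it. If the sponsor does intend an earlier lock, Section 8 should state a data cut-off, and the EFU allocation, the imputation horizon and the safety windows should be brought into line with it.
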